**Use Dec31yyyy**

Case 3: Only Year(yyyy) of the dose end date is available and yyyy = the year of EOT date:

**Use EOT date**

Case 4: Both Year(yyyy) and Month (mm) are available for dose end date, and yyyy = the year of EOT date and mm < the month of EOT date:

**Use last day of the Month (mm)**

All other cases should be considered as a data issue.

After imputation, compare the imputed date with start date of treatment, if the imputed date is < start date of treatment: Use the treatment start date

Patients with missing start dates are to be considered missing for all study treatment component related calculations and no imputation will be made. If start date is missing then end-date should not be imputed.

#### 5.1.2 AE, ConMeds and safety assessment date imputation

**Table 5-1 Imputation of start dates (AE, CM) and assessments (LB, EG, VS)**

Missing Element	Rule
day, month, and year	

• No imputation will be done for completely missing dates

day, month	

• If available year = year of study treatment start date then

Missing Element	Rule
	

○ If stop date contains a full date and stop date is earlier than study treatment start date then set start date = 01JanYYYY

○ Else set start date = study treatment start date.

● If available year > year of study treatment start date then 01JanYYYY

● If available year < year of study treatment start date then 01JulYYYY

day	

● If available month and year = month and year of study treatment start date then

○ If stop date contains a full date and stop date is earlier than study treatment start date then set start date= 01MONYYYY.

○ Else set start date = study treatment start date.

● If available month and year > month and year of study treatment start date then 01MONYYYY

● If available month and year < month year of study treatment start date then 15MONYYYY

**Table 5-2      Imputation of end dates (AE, CM)**

Missing Element	Rule (*=last treatment date plus 30 days not > (death date, cut-off date, withdrawal of consent date))
day, month, and year	

• Completely missing end dates (incl. ongoing events) will be imputed by the end date of the on-treatment period*

day, month	

• If partial end date contains year only, set end date = earliest of 31DecYYYY or end date of the on-treatment period *

day	

• If partial end date contains month and year, set end date = earliest of last day of the month or end date of the on-treatment period*

hour	

• For rATG end dates only, if partial end time contains no time, then set the time to 00:00.

Any AEs and ConMeds with partial/missing dates will be displayed as such in the data listings.

Any AEs and ConMeds which are continuing as per data cut-off will be shown as 'ongoing' rather than the end date provided.

The above imputations are only used for analyses of time to and duration of AEs and concomitant medications.

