6.1.1.2 Rabbit anti-thymocyte globulin (r-ATG)

Usually, r-ATG (Thymoglobuline[®]) will be administered at a dose of 2.5 to 3.5 mg/Kg/day on Days 1 to 5 as a slow intravenous infusion per local practice. The exact dose of r-ATG should be decided at the discretion of the investigator but should be within the above range.

Premedication with corticosteroids, acetaminophen, and/or an antihistamine 1 hour prior to each infusion of r-ATG is recommended and may reduce the incidence and intensity of infusion-associated reactions (detailed in [Section 6.2.1](#)). For the treatment for anaphylaxis and infusion-associated reactions, local label should be followed.

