6.1.5 Treatment duration

The core treatment part of this study is 6 month from the start of eltrombopag treatment (Day 1 to Week 26). Participants assessed as responders at Week 26 will be eligible to enter the extension part and may continue treatment with eltrombopag and CsA after Week 26 until Week 52.

Core treatment part

The planned duration of eltrombopag treatment is 6 months in the core treatment part. Participants may be discontinued from treatment earlier due to unacceptable toxicity, disease progression and/or treatment is discontinued at discretion of the investigator or of the participant (see [Section 9.1.1](#)).

The administration of r-ATG will be from Day 1 to Day 5.

For all participants, CsA will be administered at doses that obtain the target trough level range for 6 months if well tolerated. CsA dose may be interrupted temporarily when clinically indicated at the discretion of the investigator or treating physician. The parenteral route of administration may be used temporarily for CsA administration if indicated. Temporary interruptions for transient toxicities or dose adjustments will be reported. Per protocol interruptions will not be reported as deviations.

Extension part

The participants assessed as responders at Week 26 are eligible to enter the extension part. Eltrombopag will be provided up to Week 52 for the participants who enter the extension part and are considered to require continued treatment. For the participants who meet the discontinuation criteria in [Section 9.1.1](#), the study treatment will be discontinued.

In extension part, CsA will last for at least 18 months after Week 26 if well tolerated (total duration is from Day 1 to at least Year 2). CsA will be maintained or tapered based on the discretion of the investigator according to local practice. It is recommended that CsA treatment dose last for at least 3 months after achieving the best hematologic response, and after that CsA is recommended to be tapered by 0.3 mg/kg every month or 1 mg/kg every 3 months. CsA dose may be decreased or interrupted temporarily when clinically indicated at the discretion of the investigator or treating physician. Temporary interruptions for transient toxicities or dose adjustments will be reported. Per protocol interruptions will not be reported as deviations. After Year 2 (Week 104), CsA administration will be at the discretion of the investigator, and will not be provided within the trial anymore.

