Eltrombopag dose may be interrupted when clinically indicated at the discretion of the investigator. Interruptions will be reported. For participants who meet any toxicity criteria (see [Section 6.5.1](#)) or who do not tolerate the protocol-specified dosing schedule, the investigator will follow the guideline on dose modification and/or discontinuation presented in [Section 6.5.1](#).

Participants in whom the treatment is assessed as effective at Week 26 may continue treatment with eltrombopag and CsA after Week 26 (in the extension part of the study). Eltrombopag will be provided for the participants who entered the extension part and are considered to require continued treatment up to Week 52. The daily dose of eltrombopag in extension part is shown in [Table 6-3](#) and [Table 6-4](#).

R-ATG

R-ATG will be administered intravenously on Days 1-5. Dosing of r-ATG is defined in [Section 6.1.1.2](#).

Administer r-ATG under strict medical supervision in a hospital setting, and carefully monitor participants during the infusion. The infusion time may vary based on the participant and circumstances. Administer the first dose of r-ATG over a minimum of 6 hours; administer doses on subsequent days over at least 4 hours.

Premedication with corticosteroids, acetaminophen, and/or an antihistamine 1 hour prior to each infusion of r-ATG is recommended and may reduce the incidence and intensity of infusion associated reactions. Prior to the administration of r-ATG, a daily threshold (pre-transfusion) platelet count of $20 \times 10^9/L$ should be used for the duration of the r-ATG course.

Instructions for reconstitution, dilution and infusion from the local label should be followed strictly.

CsA

CsA will be administered orally, every 12 hours. Participants will be instructed to take CsA at the same time each day. Dosing of CsA is described in [Section 6.1.1.3](#).

CsA will be supplied as soft-gelatin capsules or as an oral solution. Switching from the soft-gelatin capsules to the oral solution should be performed with caution and under close physician supervision. The introduction of the new formulation must be made with monitoring of blood levels of CsA to ensure that pre-conversion levels are attained.

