## Document History – Changes compared to previous final version of SAP

Date	Time point	Changes	Section and title impacted (Current)
15-Sep-2020	Prior to FPFV	N/A - First version	NA
1-Jul-2022	Prior to DBL	Update the definition of on-treatment period and post-treatment period according to protocol changes; Update the windows for multiple assessments	Section 2.1.1
		Remove the race subgroup analysis in efficacy, safety and PK; Update the China Mainland/Japan specific subgroup analysis	Section 2.2.1
		Update the definition of duration of exposure with consideration of using hours as unit time for rATG; Add the definition and the corresponding statistical analysis of actual duration of exposure	Section 2.4.1
		Add the definition and the corresponding statistical analysis of actual dose intensity; Remove the planned dose intensity and relative dose intensity	Section 2.4.1
		Remove the summary analysis and the corresponding table for concomitant medications that have the potential to impact efficacy results	Section 2.4.2
		Add the supplementary analysis section to specifically describe the CR response that is derived programmatically using laboratory results	Section 2.5.1; Section 2.5.4
		Update the definition of the relapse; Add the definition and corresponding statistical analysis for below-listed item: Time to response; Maximum duration of Platelet and RBC transfusion free;	Section 2.7

Date	Time point	Changes	Section and title impacted (Current)
		Proportion of subjects with transfusion decrease; Changes in platelet count, hemoglobin and neutrophil count	
		Specify that the CTC grade $\geq 3$ adverse events will be summarized for AEs by SOC and PT	Section 2.8.1
		Add the sub-items for ALT and AST	Section 2.8.3
		Remove the percentage summary table and the shifted table for ECG Findings	Section 2.8.4.1
		Update PD and PK/PD analyses	Section 2.10
		Update the definition of the cytogenetic abnormalities and clonal evolution observed during the study; Remove the time to clonal evolution	Section 2.12
		Add the imputation rule of end dates, when missing component is the hour for rATG	Section 5.1.2

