### **Duration of exposure to study treatment**

The duration of exposure to each component (called drug X below) of the study treatment will be derived as follows:

Exposure to drug X = Last unit (date/time) of administration of X – First unit (date/time) of administration of X + (1),

where periods of drug interruption will not be deducted if there is no permanent treatment discontinuation following. If the unit is the date, then plus 1; if the unit is the hour, then transfer the exposure duration to days and plus 1 when there are residual hours.

The actual duration of exposure defines as the sum of periods where the dose exposure is non-zero.

Duration of exposure and actual duration of exposure to study treatment will be summarized for each of the study treatment components separately, using descriptive statistics (mean, standard deviation etc). For eltrombopag, the number and percentage of time on study treatment (< 3 months, 3 months to 6 months, > 6 months) will be presented. For CsA, the number and percentage of time on study treatment (< 3 months, 3 months to 6 months, > 6 months to 12

months, > 12 months to 18 months, > 18 months to 24 months) will be presented. A listing of data on subject exposure to study treatment will also be produced.

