### **Dose intensity**

Dose intensity (DI) for patients with non-zero duration of exposure is defined as follows:

DI of X (dosing unit / unit of time) = Cumulative dose of X (dosing unit) / Duration of exposure of X (unit of time).

Actual dose intensity (ADI) for patients with non-zero actual duration of exposure is defined as follows:

ADI of X (dosing unit / unit of time) = Cumulative assigned dose of X (dosing unit) / Actual duration of exposure of X (unit of time).

For patients who did not take any dose of a given drug the ADI is by definition equal to zero.

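### A missing r-ATG end time is imputed as 00:00 of the end date; if that feeds exposure, an ordinary five-day course counts as four days and its dose intensity reads 25% high

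*SAP*

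**What the plan says.** The imputation rule is the last row of Table 5-2 (end dates), identical in the primary-analysis SAP and the final-analysis SAP: "For rATG end dates only, if partial end time contains no time, then set the time to 00:00". The table is titled for adverse events and concomitant medications, and a sentence below it restricts the imputations to timing and duration analyses of those two data types.

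SAP 2.4.1 defines duration of exposure as last minus first administration, in dates or in hours. For hours it says: "if the unit is the hour, then transfer the exposure duration to days and plus 1 when there are residual hours". Dose intensity is cumulative dose divided by that duration. Both SAPs plan these summaries for each component of study treatment, r-ATG included.

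The document history of the primary-analysis SAP lists two changes in its 1-Jul-2022 revision: "Update the definition of duration of exposure with consideration of using hours as unit time for rATG" and "Add the imputation rule of end dates, when missing component is the hour for rATG".

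Section 5.1.1 of each SAP, which covers end dates of study treatment, handles missing or partial dates but says nothing about a missing time.

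On the course itself, Protocol 6.1.5 says: "The administration of r-ATG will be from Day 1 to Day 5". Protocol 6.1.1.2 says r-ATG "will be administered at a dose of 2.5 to 3.5 mg/Kg/day on Days 1 to 5". Protocol 6.7.2 says: "Administer the first dose of r-ATG over a minimum of 6 hours; administer doses on subsequent days over at least 4 hours".

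**The concern.** 00:00 is the first minute of the recorded date. Infusions on Days 2 to 5 last at least 4 hours, so one that starts and ends on the same date cannot have ended at 00:00 of that date. The imputed end precedes the start of the last infusion and removes the final dosing day from the elapsed time.

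The row also runs against the SAP's own convention. The other partial-date rows of Table 5-2 go to the latest plausible point: the last day of the year or month, capped at the end of the on-treatment period. Section 5.1.1 likewise uses the last day of the year or month, or the end-of-treatment date. Only the r-ATG time goes to the earliest point.

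At stake are the r-ATG duration and dose-intensity summaries for participants whose last r-ATG record lacks an end time. Duration would be too short and intensity too high.

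**Working it through.** **Inputs.** Planned course, Day 1 to Day 5 (Protocol 6.1.5). Hour rule and dose-intensity formula (SAP 2.4.1). Imputed time, 00:00 (SAP Table 5-2). Clock times of infusions are not in the documents, so those below are assumptions shown over a range.

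**Planned course length.** Date unit: 5 − 1 + 1 = 5 days. Hour unit with complete times, Day 1 09:00 to Day 5 15:00: 4 × 24 + 6 = 102 h = 4 days 6 h, plus 1 for the residual hours = 5 days. Both agree with the planned course.

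**With the imputed time.** Day 1 09:00 to Day 5 00:00: 96 − 9 = 87 h = 3 days 15 h, plus 1 = 4 days.

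**General result.** Let the Day 1 infusion start at clock hour s and the Day 5 infusion end the same day at clock hour e.

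- Imputed span: 96 − s hours, which lies above 72 and at or below 96, so always 4 days.
- Complete-data span: 96 + (e − s) hours. This gives 5 days if e is later than s, and 4 days if e is at or before s.

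| Day 1 start | Last infusion ends | Complete times | With 00:00 | Intensity ratio |
|---|---|---|---|---|
| 00:00 | Day 5 04:00 | 100 h, 5 days | 96 h, 4 days | 1.25 |
| 09:00 | Day 5 15:00 | 102 h, 5 days | 87 h, 4 days | 1.25 |
| 12:00 | Day 5 13:00 | 97 h, 5 days | 84 h, 4 days | 1.25 |
| 18:00 | Day 5 22:00 | 100 h, 5 days | 78 h, 4 days | 1.25 |
| 14:00 | Day 5 13:00 | 95 h, 4 days | 82 h, 4 days | 1.00 |
| 18:00 | Day 6 00:00 | 102 h, 5 days | 102 h, 5 days | 1.00 |

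**Dose intensity.** For a constant daily dose d over five days, the cumulative dose is 5d. The correct intensity is 5d/5 = d; the imputed one is 5d/4 = 1.25d. So 2.5 reads as 12.5/4 = 3.125, 3.0 as 15/4 = 3.75, and 3.5 as 17.5/4 = 4.375 mg/kg/day.

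**Alternative reading of the hour rule.** If the rule meant fractional days plus 1, the 09:00 to 15:00 example would give (4.25 + 1)/(3.625 + 1) = 5.25/4.625 = 1.135, an inflation of 13.5%. The wording reads more naturally as rounding up.

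**One-day course.** Start 09:00 and imputed end 00:00 on the same date give −9 h. The check in Section 5.1.1 that an imputed end is not before the start compares dates, so it would not catch this.

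**Effect on the summary.** If k of 36 participants are affected and doses are equal, mean dose intensity rises by 25% × k/36. For k = 4 that is 2.8%. The documents do not give k.

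**The case against.** The strongest objection is the scope sentence under Table 5-2. r-ATG is study treatment, its end dates belong to Section 5.1.1, and read literally the 00:00 rule never reaches duration or dose intensity. This stands to the extent that the exposure effect is an inference from the document history, not something the table states. It does not rescue the plan. r-ATG is neither an adverse event nor a concomitant medication, so under the literal reading the row does nothing and a missing r-ATG time has no rule.

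Two stronger readings are tempting, and the documents do not support them.

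- A reader might infer that the rule distorts every course to which it is applied. It does not: the last two rows of the table above show unchanged day counts. In the 14:00 case the 4-day count comes from the 2.4.1 formula itself, even with complete times.
- A reader might infer that a compliant course would be reported as an overdose, since 3.75 exceeds 3.5 mg/kg/day. That range governs the prescribed daily dose, and neither SAP compares dose intensity with it. Planned and relative dose intensity were removed from the SAP, and all administered doses are listed by participant. A true daily dose of 2.8 mg/kg or less would in any case read no higher than 3.5 (2.8 × 1.25 = 3.5).

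It is also fair to say that a negative span is conditional. Duration is taken from first to last administration, so it arises for a course confined to one day. It would arise more widely only if actual duration of exposure is summed from date-times of single infusions, which the documents do not say.

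**Conclusion.** The point holds as a minor defect. On either reading the SAP needs correcting: the r-ATG row gives a wrong end time for a same-day infusion, or it has no function and leaves a gap.

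If it feeds the hour-based exposure, the error is one day in five and +25% in dose intensity. This happens when the last infusion ends on Day 5 at a later clock time than the Day 1 infusion started. It rests on the rounding-up reading of the hour rule and on a record with a missing end time.

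The consequence is confined to descriptive r-ATG exposure and dose-intensity summaries, for an unknown number of records. The primary endpoint and the other efficacy analyses are untouched.

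**What to change.** In both SAPs:

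1. Move the r-ATG time row from Table 5-2 to Section 5.1.1, or exempt it explicitly from the sentence that limits the table's scope. Changing the cell alone would leave that sentence and Section 5.1.1 unreconciled.
2. Replace 00:00 with the recorded start time of that infusion plus the protocol minimum infusion time (6 h for the first dose, 4 h for later ones). If the start time is also missing, use 23:59 of the recorded end date. Alternatively, use the date-unit formula, last date minus first date plus 1, for these records.

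The cost is a few lines of text in each SAP and one programmed derivation, with no new data. There is a small downside: 23:59 can overstate duration by one day when the true end is at or before the Day 1 start clock time. With Day 1 14:00 and a true end of Day 5 13:00, complete times give 4 days and 23:59 gives 5. In the 09:00 example, 23:59 gives 5 days, as complete data would.

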#### **5.1.2.1    Other imputations**

#### **Incomplete date of initial diagnosis of SAA**

Missing day is defaulted to the 15th of the month and missing month and day is defaulted to 01-Jan.

### **5.2      AEs coding/grading**

Adverse events are coded using the Medical dictionary for regulatory activities (MedDRA) terminology.

AEs will be assessed according to the Common Terminology Criteria for Adverse Events (CTCAE) version 4.03.

The CTCAE represents a comprehensive grading system for reporting the acute and late effects of cancer treatments. CTCAE grading is by definition a 5-point scale generally corresponding to mild, moderate, severe, life threatening, and death. This grading system inherently places a value on the importance of an event, although there is not necessarily proportionality among grades (a grade 2 is not necessarily twice as bad as a grade 1).

### **5.3      Laboratory parameters derivations**

Grade categorization of lab values will be assigned programmatically as per NCI Common Terminology Criteria for Adverse Events (CTCAE) version 4.03 (specify version used in the RAP). The calculation of CTCAE grades will be based on the observed laboratory values only, clinical assessments will not be taken into account. The criteria to assign CTCAE grades are given in Novartis internal criteria for CTCAE grading of laboratory parameters. The latest

available version of the document based on the underlying CTCAE version 4.03 at the time of analysis will be used.

For laboratory tests where grades are not defined by CTCAE v4.03, results will be graded by the low/normal/high (or other project-specific ranges, if more suitable) classifications based on laboratory normal ranges.

A severity grade of 0 will be assigned for all non-missing lab values not graded as 1 or higher. Grade 5 will not be used. For laboratory tests that are graded for both low and high values, summaries will be done separately and labelled by direction, e.g., sodium will be summarized as hyponatremia and hypernatremia.

### **Imputation Rules**

CTC grading for blood differentials is based on absolute values. However, this data may not be reported as absolute counts but rather as percentage of WBC.

If laboratory values are provided as ‘<X’ (i.e. below limit of detection) or ‘>X’, prior to conversion of laboratory values to SI unit, these numeric values are set to X.

The following rules will be applied to derive the WBC differential counts when only percentages are available for a xxx differential

$$\text{xxx count} = (\text{WBC count}) * (\text{xxx \%value} / 100)$$

CTCAE grades for the derived absolute WBC differential counts will be assigned as described earlier.

## **5.4 Statistical models**

### **5.4.1 Primary analysis**

Responses will be summarized in terms of percentage rates with 95% CIs. An exact binomial confidence interval (implemented using SAS procedure FREQ with EXACT statement for one-way tables) will be calculated ([Clopper and Pearson, 1934](#)).

SAS procedure FREQ will be used to estimate the proportion of responders, along with the associated 95% ( $=100 \times (1 - \text{two-sided alpha level})$ ) two-sided Pearson-Clopper CI.

### **5.4.2 Secondary analysis**

#### **Kaplan-Meier estimates**

For time to event endpoints (time to response, duration of response etc.), an estimate of the survival function will be constructed using Kaplan-Meier (product-limit) method as implemented in PROC LIFETEST with METHOD=KM option.

Quartiles of the survival function, if reached, will be obtained along with 95% confidence intervals calculated from PROC LIFETEST output using the method of ([Brookmeyer and Crowley, 1982](#)). Kaplan-Meier estimates of the survival function with 95% confidence intervals at specific time points will be summarized. The standard error of the Kaplan-Meier estimate will be calculated using Greenwood's formula ([Collett, 1994](#)).

